### **Background and Rationale**

Complicated diverticulitis with peritonitis (Hinchey III–IV) remains a condition characterized by marked intraoperative decision-making variability, in the absence of standardized criteria to guide the choice between primary anastomosis and Hartmann's procedure. Artificial intelligence (AI) and computer vision are emerging tools that may integrate clinical data and intraoperative images in order to support the surgeon during the decision-making process.

This study does not involve any therapeutic intervention and does not modify current clinical practice.

### **Objectives**

#### **Primary Objectives**

- To reduce the colostomy rate in patients undergoing emergency surgery for acute complicated diverticulitis.
- To collect clinical data and intraoperative images/videos from patients undergoing emergency surgery for acute complicated diverticulitis, in order to identify the factors influencing the choice between primary anastomosis and Hartmann's colostomy, and to reproduce such decision-making patterns through AI algorithms.
- To develop a software tool capable of analyzing intraoperative images according to predefined parameters in order to estimate the risk of complications when performing left colectomy with anastomosis.

The data collected in this phase will constitute the basis for the future development of a standardized dataset to support the creation of decision-support tools in subsequent phases.

### **Secondary Objectives**

- To identify the clinical and intraoperative parameters that influence surgical decision-making.
- To assess the quality and feasibility of intraoperative image/video collection across the participating centers.
- To explore the role of fluorescence imaging (ICG) in intraoperative bowel perfusion assessment and in the surgeon's decision-making process.

### **Study Design**

This is a multicenter, observational, non-interventional study.

It includes both retrospective and prospective patients undergoing emergency colorectal resection through a minimally invasive approach.

The following data will be collected:

- Clinical data (demographics, comorbidities, imaging findings, intraoperative parameters, outcomes);
- Visual data (anonymized laparoscopic or robotic images/videos);
- Surgical reasoning (factors that guided the intraoperative decision).

The study does not alter the diagnostic or therapeutic pathway, nor does it interfere with operating room workflow. Patient treatment will remain fully consistent with standard clinical practice.

### **Inclusion Criteria**

- Age  $\geq 18$  years
- Informed consent obtained before data collection and acquisition of surgical images/videos, in accordance with local regulations
- Acute complicated diverticulitis requiring urgent surgery
- Minimally invasive surgical approach (laparoscopic/robotic)
- Hartmann's procedure or resection with anastomosis ( $\pm$  ileostomy)

### **Exclusion Criteria**

- Open surgery
- Non-diverticular disease
- Lack of informed consent

## **Endpoints**

### **Primary Endpoint**

Creation of a structured clinical and visual dataset, obtained through the prospective collection of clinical data and intraoperative images/videos from patients undergoing emergency surgery for complicated diverticulitis, aimed at analyzing the factors influencing the intraoperative choice between primary anastomosis and Hartmann's procedure, with the long-term goal of reproducing this decision-making process through AI algorithms.

### **Secondary Endpoints**

- Frequency and quality of image acquisition for each predefined surgical phase
- Descriptive analysis of observed decision-making patterns (anastomosis vs Hartmann)
- Postoperative outcomes (anastomotic leak, complications, stoma management)
- Assessment of the technical and organizational feasibility of multicenter collection of standardized clinical and visual data

## **Data Collection, Management, and Storage**

### **Site of Data Collection**

Data will be collected exclusively at authorized participating clinical centers.

At each center:

- clinical data will be obtained from the medical records;
- images/videos will be obtained from laparoscopic or robotic platforms;
- the surgeon's report form will be completed at the end of the procedure.

The sponsor center, IRCCS San Raffaele, will be responsible for receiving the data and performing the related analyses.

### **Data Collection Procedures**

Sixty-three centers have agreed to contribute to the collection of clinical and intraoperative visual data.

Each center will:

- extract clinical data in anonymized form;
- export images/videos without metadata, including no patient name, date/time, or procedure number;
- assign a unique AIDE-XXX code to each case;
- upload the data to a secure portal or send them on encrypted storage media.

The re-identification key will remain at the originating center and will not be transferred.

### **Data Storage**

Anonymous data will be stored on a secure GDPR-compliant server. No data will be uploaded to non-European or non-GDPR-compliant cloud services.

### **Data Access**

Access will be restricted exclusively to the PI and co-investigators at the coordinating center.

### **Data Transfer Between Centers**

Only anonymized data will be transferred, through a secure platform or encrypted physical media (USB drive/hard disk).

### **Data Retention Period**

Data will be retained for 10 years after study closure, in accordance with Italian and European regulations applicable to observational studies.

### **Purpose of Data Use**

The data collected in this study phase will be used exclusively for:

- observational scientific research purposes;
- analysis of the clinical and intraoperative factors guiding surgical decisions in patients with complicated diverticulitis;
- scientific publications in aggregated and fully anonymized form.

No commercial use is planned.

Any future developments, including predictive models based on artificial intelligence, will be the subject of specific protocols requiring new ethical approval.

## **Sample Size**

As this is a pilot study, no formal sample size calculation is required. However, the aim is to collect approximately 150 cases (75 Hartmann's procedures and 75 anastomoses).

Recruitment will be competitive. Each center will contribute data from at least 5 cases.

Descriptive statistical analyses and implementation of AI algorithms are planned.

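### The 75/75 target is set on the decision under study, with no consecutive-case rule or count of eligible cases, so the sample split cannot be read as a practice frequency

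*Protocol*

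**What the plan says.** The Sample Size section gives no calculation ("As this is a pilot study, no formal sample size calculation is required") and then sets a target by procedure: "the aim is to collect approximately 150 cases (75 Hartmann's procedures and 75 anastomoses". On accrual it says only: "Recruitment will be competitive. Each center will contribute data from at least 5 cases".

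The variable that defines the split is also the one being studied. One of the Primary Objectives is to find what drives the choice of procedure and "to reproduce such decision-making patterns through AI algorithms". The Primary Endpoint is a dataset built for the same purpose. Among the Secondary Endpoints is "Descriptive analysis of observed decision-making patterns (anastomosis vs Hartmann".

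Two further statements bear on how the target could be filled. Under Study Design: "It includes both retrospective and prospective patients undergoing emergency colorectal resection through a minimally invasive approach". Under Data Collection Procedures: "Sixty-three centers have agreed to contribute to the collection of clinical and intraoperative visual data".

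The protocol does not say whether 75/75 is a recruitment goal to be enforced or the split the sponsor expects to see. It has no rule for what happens when one group is full, no requirement that cases be consecutive, and no record of eligible cases that were not entered.

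**The concern.** A target number for each level of the outcome is outcome-dependent sampling, as in a case-control study. That is a legitimate design for comparing factors between two groups. It cannot also show how often each choice is made, because that frequency has been set in advance.

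The protocol leaves room for the target to be met by selection. In a retrospective case the procedure is known before the case is chosen. Competitive recruitment with a per-procedure aim lets centers supply whichever group is short. If all 63 centers contributed the stated minimum of 5, there would be 63 × 5 = 315 cases against an aim of about 150, so a surplus to choose from is possible.

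Three readings are at stake: the Hartmann share, its variation between centers, and the probability of Hartmann produced by any algorithm trained on the data. If inclusion within a group also depended on the factors under study (for example, cases with better documentation or clearer images), the factor associations would be affected too.

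**Working it through.** **The plan's own figure.** 75 + 75 = 150, and 75/150 = 50% Hartmann. The protocol states no alpha, power, effect size or event rate, so there is nothing further to reproduce.

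**Assumption.** The true Hartmann share among eligible cases, π, is not in the protocol. It is varied from 30% to 80%.

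**Step 1: would unselected accrual give about 75/75?** With X ~ Binomial(150, π), compute P(70 ≤ X ≤ 80).

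**Step 2: how many eligible cases are needed to reach 75 of the rarer procedure?** N = 75 / min(π, 1 − π). Cases left out = N − 150. At π = 30%: 75/0.30 = 250 eligible. Of these, 250 × 0.70 = 175 are anastomoses, and 175 − 75 = 100 are not used.

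**Step 3: how far do predicted probabilities of Hartmann move?** With equal numbers sampled, logit(sample) = logit(true) + log[(0.5/0.5) / (π/(1 − π))]. At π = 30% the shift is log(0.7/0.3) = 0.847. A patient with a true probability of 30% is then predicted at 50%. At π = 70% the shift is −0.847, and the same patient is predicted at about 15%.

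| True Hartmann share (assumed) | P(70 to 80 Hartmann in 150) | Eligible cases needed | Left out | Logit shift | True 0.20 / 0.50 / 0.80 predicted as |
|---|---|---|---|---|---|
| 30% | <0.001 | 250 | 100 | +0.85 | 0.37 / 0.70 / 0.90 |
| 40% | 0.057 | 188 | 38 | +0.41 | 0.27 / 0.60 / 0.86 |
| 50% | 0.63 | 150 | 0 | 0 | 0.20 / 0.50 / 0.80 |
| 60% | 0.057 | 188 | 38 | −0.41 | 0.14 / 0.40 / 0.73 |
| 70% | <0.001 | 250 | 100 | −0.85 | 0.10 / 0.30 / 0.63 |
| 80% | <0.001 | 375 | 225 | −1.39 | 0.06 / 0.20 / 0.50 |

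Unless practice is close to 50/50, the target is therefore either met by selection or missed.

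**Step 4: what does not move?** Take a factor present in 60% of Hartmann and 30% of anastomosis cases. The odds ratio is (0.6/0.4)/(0.3/0.7) = 3.5 in the source population. It is also 3.5 in a 75/75 sample, provided cases within each group are chosen without regard to the factor.

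**Step 5: can the shift be undone?** Yes, if eligible cases were counted. At π = 30%, each sampled anastomosis stands for 175/75 = 2.33 eligible cases and each Hartmann case for 75/75 = 1. Since log(2.33) = 0.85, these weights remove exactly the shift in Step 3.

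**The case against.** The strongest reply is that the text states an aim and an approximate total. It names no cap and no closing of a full group. If 75/75 is only the expected split, the observed frequencies do reflect practice. This stands. A reader might infer a fixed quota, or that centers will hand-pick cases, but the protocol says neither. It allows selection without describing it.

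Other parts of the reply also stand:

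- Finding the factors behind the choice is the central analytic aim, and a balanced sample suits it. Step 4 shows that odds ratios are not biased by outcome sampling as such.
- A reader might infer that every predicted probability is affected. The risk tool named in the Primary Objectives estimates complications given anastomosis, and the ratio between the two procedures does not set that risk.
- The shift might be taken as permanent. It is a single offset, recoverable once the true share is known.
- No endpoint expressly promises a Hartmann proportion. Purpose of Data Use defers predictive models to later protocols, although the Primary Objectives and Sample Size sections bring AI algorithms into this study.

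The reply does not dispose of the point. Weighting and recalibration can be left to a statistical analysis plan, but both need a count of eligible cases by procedure. That count has to be arranged before data collection, and nothing in the protocol does so. The descriptive report of decision patterns in this study also invites the reader to take the sample split as practice.

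**Conclusion.** The point holds in a conditional form and should be settled before data collection. The target is defined on the decision under study, and the protocol has neither a consecutive-case rule nor a denominator. If the target is reached by selection, the Hartmann share is 50% by design. Uncorrected decision probabilities then shift by 0.41 on the logit scale at an assumed 40/60 split and by 0.85 at 30/70. If practice is itself 50/50 there is no shift. The true share is an assumption throughout.

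The documents do not support the wider claims that a quota is enforced, that all predicted risks are wrong, or that the factor associations are biased. Those associations are safe only if selection within each group is unrelated to the factors, which the protocol does nothing to ensure.

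**What to change.** In the Sample Size section:

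1. State that 75/75 is a recruitment target and not an estimate of how often each procedure is chosen.
2. Within each center and a declared period, enter eligible cases consecutively, retrospective and prospective alike, until the group is full.
3. Have each center log the number of eligible cases by procedure over that period, including those not entered.
4. Take the Hartmann share and its between-center variation from the log, and use the log to weight, or to correct the intercept of, any model of the decision.
5. Where no log exists, do not report the sample split as a practice frequency.

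The cost is a short count log at each center and slightly more analysis. The balance, and the retrospective cases that Study Design admits, can be kept.

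Dropping the split and taking 150 consecutive cases is an alternative, but it is a real trade-off. If Hartmann made up 70% of cases, anastomoses would fall from 75 to 150 × 0.30 = 45. Standard errors in that group would be about √(75/45) = 1.29 times as large, which would hurt the complication-risk objective. The log answers the point without that loss.

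### A minimum of 5 cases from each of 63 centers implies at least 315 cases, 2.1 times the stated aim of about 150

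*Protocol*

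**What the plan says.** Two sections of the protocol fix the size of the study.

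- **Sample Size**, on the total: "the aim is to collect approximately 150 cases (75 Hartmann's procedures and 75 anastomoses". The section gives no power calculation and says why: "As this is a pilot study, no formal sample size calculation is required".
- **Sample Size**, on how cases will arrive: "Recruitment will be competitive", followed at once by "Each center will contribute data from at least 5 cases".
- **Data Collection Procedures**, on the number of centers: "Sixty-three centers have agreed to contribute to the collection of clinical and intraoperative visual data". A list of duties that fall on each center follows directly.

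Nothing in the protocol limits the 5-case minimum to some of the centers, says that fewer than 63 will contribute, or describes 150 as a lower bound.

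**The concern.** The total, the number of centers and the minimum per center are tied together by simple multiplication: any two of them constrain the third. Here the center count and the minimum lead to a total far above the one stated, and the two statements stand in different sections, so the conflict is easy to miss.

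Because there is no formal sample size calculation, these figures are the only statement of how large the study will be. As they stand, a center or an ethics committee cannot tell whether the plan is to collect records and videos from about 150 patients or from at least 315. A center also cannot tell whether 5 cases is a commitment it must meet or a figure that most centers are not expected to reach. The 75 and 75 target by procedure is tied to the smaller total only.

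**Working it through.** **Inputs, all from the protocol**

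| Input | Value | Section |
|---|---|---|
| Aim for the total | about 150 | Sample Size |
| Split by procedure | 75 and 75 | Sample Size |
| Minimum per center | 5 | Sample Size |
| Recruitment mode | competitive | Sample Size |
| Centers that have agreed | 63 | Data Collection Procedures |

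**Step 1. Reproduce the stated total.** 75 + 75 = 150. The total agrees with its own split, so the fault does not lie there.

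**Step 2. Total implied by the minimum.** Centers x minimum = 63 x 5 = 315. Since 5 is a minimum, 315 is a lower bound.

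**Step 3. Size of the gap.** 315 - 150 = 165 cases; 315 / 150 = 2.1.

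**Step 4. Work back from 150.**

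- Mean per center if all 63 contribute: 150 / 63 = 2.38, less than half the stated minimum.
- Largest number of centers that can each give 5 cases: 150 / 5 = 30.
- Those 30 as a share of the centers that agreed: 30 / 63 = 48%.
- Centers left below 5, if all 63 contribute and collection ends at about 150: at least 63 - 30 = 33.

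**Step 5. What would make the figures agree.** Each line holds two of the three figures and solves for the other.

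| Held fixed | What must change |
|---|---|
| about 150 cases, 63 centers | the minimum of 5 goes; the average is about 2.4 |
| about 150 cases, minimum 5 | about 30 centers at most |
| 63 centers, minimum 5 | total of at least 315 |

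The protocol states none of these three resolutions.

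**The case against.** The strongest defence is that the total is soft. It is an aim and an approximate one, in a pilot study, and the protocol gives no rule that collection stops there. If 150 is only a goal, all 63 centers could meet their minimum and the study would overshoot. A second defence is that agreeing to contribute is not the same as contributing: the section on the site of data collection speaks of authorized participating centers, and if about 30 became active the figures would fit.

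Both defences have some force, but neither removes the mismatch. An approximate aim covers modest variation, not a total 2.1 times as large. The second reading needs more than half of the centers to drop out, which the protocol nowhere says; its wording on the minimum covers every center.

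What stands of the objection limits how far the point can be taken. A reader might infer any of the following, and the protocol does not support them:

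- *That enrolment closes at 150, so the minimum is impossible.* Competitive recruitment usually means that centers enrol until a common total is reached, but the protocol neither defines the term nor gives a stopping rule.
- *That 33 centers are bound to miss the minimum.* That number holds only if all 63 contribute and collection ends at about 150.
- *That too few cases per center will prevent center habit from being separated from patient factors.* The protocol states no center-level or center-adjusted analysis. It plans descriptive statistics and AI algorithms.
- *That the minimum will push small centers to supply selected past cases.* Retrospective patients are allowed, but nothing in the text links the minimum to how cases are chosen.

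**Conclusion.** The point holds as an inconsistency between the Sample Size and Data Collection Procedures sections. Read at face value, with all 63 centers contributing and the minimum applying to each, the protocol commits to at least 315 cases while aiming for about 150: 165 more, or 2.1 times as many. The planned size and the per-center contribution cannot be delivered together.

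The result rests on two readings, both of which follow the text: that the 63 centers that agreed are those that will contribute, and that 150 is the intended size rather than a lower bound. The arithmetic needs no outside figure.

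The consequences are for planning and feasibility. The study is an observational pilot without a formal sample size calculation, so no power, type I error or treatment exposure is affected. It would also go too far to conclude that 150 is the correct figure and the minimum the mistaken one. Nothing in the protocol shows which of the three was intended.

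**What to change.** Restate the total, the number of contributing centers and the minimum per center so that they agree. The sponsor has to say which of them is meant.

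- **Keep about 150 and all 63 centers.** Replace the 5-case minimum with an expected average of 2 to 3 cases per center. No extra cases. The cost is a less favourable statement of the data from each center.
- **Keep about 150 and the minimum.** State that about 30 of the 63 centers will contribute. No extra cases. The cost is a smaller stated number of contributing centers.
- **Keep 63 centers and the minimum.** Change the total to at least 315 and restate the 75 and 75 split to match. This means at least 165 cases beyond the present aim.

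Any of these is a one-paragraph amendment. It would help to say in the same paragraph whether collection ends when the total is reached, since the protocol leaves competitive recruitment undefined. A cap on cases per center is not needed to resolve the inconsistency.

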## **Ethical Aspects**

This is a non-profit, observational study, with no additional therapeutic or diagnostic intervention.

No additional risk is expected for participating patients.

Clinical data and videos collected for the study will be anonymized and coded according to the procedures established by the participating centers.

Images and videos will be stripped of any identifying elements, including face, voice, and sensitive data.

Written informed consent for the use of data for research purposes will be obtained by the recruiting clinical centers.

The study complies with the GDPR and with applicable national regulations concerning personal data protection.

Study results will be disseminated in aggregated and anonymized form and used exclusively for scientific research purposes.

The data collected will help improve understanding of intraoperative decision-making factors in patients with complicated diverticulitis.

Any future developments, including AI-based decision-support models, will be addressed through separate protocols to be submitted for independent ethical review.
